It is widely postulated in the literature that ¹⁸F-fluorodeoxyglucose (FDG) imaging can improve risk assessment and prognostication through the identification of high-risk "vulnerable" plaques, plaques that demonstrate heightened inflammation, neovascularization or apoptosis. The primary target is the carotid and coronary arteries, imaging will also include the ascending and descending aorta, and the iliac arteries. Successful FDG PET imaging has been performed in large vascular beds, including the carotid arteries, and recent preliminary reports suggest the potential for noninvasive coronary plaque imaging. The advantage of nuclear imaging is that multiple vascular beds can be imaged with a single radionuclear isotope administration.

In a subset of 60 individuals we plan to study the reproducibility of arterial stenosis and plaque volume as measured by MDCTA.

At present, there is no available data on the reproducibility of 320 detector row MDCT for measuring arterial stenosis and plaque volume. This data will allow investigators to determine whether measured changes in stenoses and plaque morphology exceed that expected from the limits of measurement error in CTA and thus make the results of ongoing trials more reliable.

Consistent with such objectives, our specific aims are:

1st Aim

To examine whether image guided lipid lowering therapy is superior to NCEP guided therapy in promoting carotid atherosclerotic plaque regression and stabilization.

2rd Aim

To investigate whether the observed change in carotid atherosclerosis volume measured by MR, parallels observed change in coronary atherosclerosis volume measured by MDCT angiography.

3rd Aim

To examine whether MRI guided plaque regression and stabilization produces greater reduction in clinical CV events than standard NCEP guided therapy.

4th Aim

To examine the statin dosages required to promote plaque regression and stabilization differ between conventional and image guided strategies.

5th Aim

To investigate whether FDG PET activity predicts carotid morphological plaque regression and stabilization in both the carotid and coronary arteries and compare the efficacy of PET based prediction with MRI.

6th Aim

To correlate FDG uptake in the carotid, coronary, aortic, and iliac arteries with absolute values and changes in hematological biomarkers of vascular inflammation, thrombosis and atheroprotection at and between each time point.

7th Aim

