A subgroup of 60 patients will be recruited to participate in PET scanning which will be performed twice, once at study initiation and after 6 months of trial-directed statin therapy.

Information including cardiovascular risk factors and other medication, including anti-inflammatory drugs, use will be collected. The total cholesterol and LDL levels and the dosage of statins required to achieve that target will be recorded.

Inclusion Criteria:

Participants who are not participating in the CT Reproducibility study are eligible.

Exclusion Criteria:

Patients who are unable or unwilling to comply with the physical activity restrictions or fast for 12 hours prior to FDG PET scanning will be excluded. Due to the need for dietary manipulation and the maintenance of strict glycemic control we will exclude diabetic patients from our initial study sample. Blood glucose measurements before injection must be within normal limits, less than 200 mg/dL (11 mmol/L).

Hematological Biomarkers Markers:

Blood tests for inflammatory markers will be incorporated into the baseline and 6 month blood draws. Standard investigations will include C-reactive protein, matrix metalloproteinase -3 and -9, interleukin-18, cathepsin K, fibrinogen, adiponectin, and plasminogen activator.¹²⁻¹³ A tube of blood will be stored at -70°C for testing of further markers defined at a later date.

FDG PET Preparation:

Study subjects will be asked to fast for 12 hours prior to PET scan. On the morning of the PET study, a low carbohydrate meal will be provided to study participants. Patients will be asked to avoid exercise 24 hours prior to scanning.

Carotid and Cardiac FDG PET Imaging Technique: On the morning of the scan, Metoprolol 50 - 100 mg PO will be administered to slow the heart rate and optimize the acquisition of diastole.¹

The dose of FDG administered, duration between FDG injection and PET image acquisition, and the method of quantification of FDG uptake will be standardized.¹⁵ The injected dose of 18F-fluorodeoxyglucose will be 5.2 MBq/kg (140 mCi/kg) of lean body mass to a maximum of 12.5 mCi.

Patients will be kept resting comfortably in a semi-dark room. Scanning will be initiated after 90 minutes.¹⁶⁻²⁰ Typically, extended time imaging will be performed of the coronary and carotid beds first, followed by a 5 - 15 minute break and imaging of the remainder of the body.

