The initial acquisition will centered over the heart in 3-dimensional mode for at least 20 minutes. When feasible, both cardiac and respiratory gating will be performed. Images will be acquired in list-mode allowing for both single phase and segmented reconstructions.

Subjects will be placed in a head holder and mobility-restricted with padding and tape-reminders. Using ultrasound, performed prior to the FDG injection, the carotid bifurcation will be located and a single-bed position high-resolution carotid PET scan will be performed using 3D mode with a minimum acquisition time of 9 minutes.²¹

After a short break, lasting 5 – 15 minutes, body PET scanning will be performed. Body imaging will use standard 3D mode techniques and will consist of sequential emission images obtained with 16 cm fields of view each acquired over at least a 2 minute interval. Scanning will extend from the skull base to mid-thigh obtained in the cranial-caudal direction.

CT imaging or MRI is necessary for attenuation correction and signal localization.

CT / MR Acquistion:

All studies will be performed according to routine protocol using a dedicated PET/CT system, or when available, a dedicated MR/PET. These devices are comprised of a PET scanner coupled to either a multislice CT or MRI scanner. With PET/CT, the PET and CT components are mounted back-to-back and mechanically calibrated to ensure alignment of the CT and PET planes; the imaging protocol consists of an initial CT acquisition followed by the PET study. During 2011, the NIH is slated to receive the Siemens Biograph mMR (molecular MR) which is the first integrated MR/PET scanner; this state-of-the-art machine incorporates a ring of lutetium oxy-orthosilicate crystal PET detectors inside the bore of a 3T MRI magnet and allows for simultaneous MRI and PET acquisitions.

CT or MRI scanning will be performed from skull base to mid-thighs using appropriate respiratory and cardiac gating. CT parameters (Biograph, Siemens PET/CT) include a spiral acquisition using 120 kVp and 115 mA with a section thickness of 2.5 mm; no oral or intravenous contrast material will be administered for the CT. The MR acquisition (Verio, Seimens) will employ the Total imaging matrix (Tim) coil technology using standard parameters with field of view and matrix size adjusted to the imaged body part.

High Resolution Carotid MRA:

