In order to facilitate the comparison between MRI and PET imaging prior to the availability of the integrated MR/PET unit, an additional high resolution carotid MRA examination will be performed at the 6 month time point. This gadolinium enhanced study will use the standard carotid MRA study protocol and be scheduled on the same day or within a 2 week interval from the PET scan. Carotid positioning will be reproduced through positioning technique using careful measurement, such as the distance between the chin and sternal notch, and employing mobility-restricting equipment, like the head holder and tape reminders.

Image Reconstruction and Registration of Carotid and Cardiac FDG PET Imaging:

PET image reconstruction will use standard filters for a fully iterative process using optimized spectral content measure with at least 2 iterations and 28 subsets. High resolution reconstruction of the neck will be performed using at least 256 x 256 matrices; other vascular beds will be reconstructed using at minimum the standard 128 x 128 matrices.

Matching PET/CT and MR/PET images will be fused.¹¹ Both vendor specific software and open source programs will be used for region of interest delineation for partial volume correction and for vessel wall and lumen for calculation of vessel wall FDG uptake.²²

Imaging of the thorax will be viewed as both summed and gated reconstructions. For the gated reconstruction, 8-frames per cardiac cycle will be binned and the usable frames from middle to late diastole that have minimal blurring will be extracted and summed to enhance count density of the coronary arteries and warped for co-registration with the diastolic and respiratory gated CT / MR data.

Data Analyses of FDG PET Imaging:

For each patient scan, quantitative analysis will be performed of carotid and coronary arteries, aortic arch, ascending and descending aorta, abdominal aorta and iliac vascular territories. Arterial wall lesions with radioactivity concentrations above the mean blood-pool activity, and/or with calcification detected by CT and with morphology consistent with that of a plaque will be considered plaque and included in the assessment. CT / MR evaluation will be performed to identify atherosclerotic plaque as abnormal wall thickening with or without the presence of other features, like a lipid core or focal calcification, on a segment by segment basis. Maximum standardized uptake value (SUV_{max}) corrects for patient weight and injected dose-decay:

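### Nothing ties a participant's baseline and 6-month PET scans to the same system, so in any mixed pair the FDG change combines a scanner difference with the change on statin therapy

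*Combined protocol and SAP*

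**What the plan says.** The PET Substudy is described in section 1.3 Design. Its size is given as "A subgroup of 60 patients will be recruited to participate in PET scanning", and PET is "performed twice, once at study initiation and after 6 months of trial-directed statin therapy".

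On equipment, the CT / MR acquisition paragraph says "All studies will be performed according to routine protocol using a dedicated PET/CT system, or when available, a dedicated MR/PET". It adds "During 2011, the NIH is slated to receive the Siemens Biograph mMR (molecular MR) which is the first integrated MR/PET scanner". The paragraph on the high-resolution carotid MRA covers the period "prior to the availability of the integrated MR/PET unit, an additional high resolution carotid MRA examination will be performed at the 6 month time point". The plan thus expects some scanning before the new unit arrives and some after. On attenuation correction, it says "CT imaging or MRI is necessary for attenuation correction and signal localization", so the method can depend on the system used.

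The plan standardizes FDG dose, the interval from injection to acquisition, and the method of quantification. Reconstruction settings are given only as minimum values.

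In section 6.0, the paragraph for Hypotheses 5, 6 and 7 compares findings within and between the baseline and 6-month time points. It correlates imaging findings and their changes with statin dose, lipids and biomarkers. Aim 6 in section 1.2 relates FDG uptake to "absolute values and changes in hematological biomarkers of vascular inflammation". None of these passages mentions which PET system was used.

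**The concern.** A within-person change in FDG uptake can be read as a response to therapy only if the measuring instrument is the same at both visits, or if the difference between instruments is known and removed. The plan allows the instrument to change and supplies no control for it: no same-system rule, no PET cross-calibration or phantom, no matching of reconstruction across systems, no recording of the system, and no model term.

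The plan does take this care elsewhere. Each coronary CT includes a phantom to correct density between scans, and the CT reproducibility scan repeats the same methods.

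At stake are the baseline-to-6-month change in SUVmax and TBR and its correlations with lipids, dose and biomarkers. Any analysis of within-person variability under Aim 7 is also exposed, because a device difference would be counted as variability in the person. The 6-month scan is always the scan after trial-directed therapy. In pairs that move to the new system, device and treatment period therefore change together.

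**Working it through.** The documents give no power or precision figure for the PET substudy, so there is nothing to reproduce. The check is a reading of the text followed by an illustration.

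**Text check**

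1. Can the two scans of one person use different systems? Yes. Either system is permitted, a transition is foreseen, and no passage restricts a participant to one.
2. Can the system affect the measurement? The plan itself allows CT-based or MR-based attenuation correction and does not state that reconstruction is matched across systems. The size of any effect is not given.
3. Does the analysis account for it? No scanner term, stratification or exclusion appears in section 6.0.
4. Can a control group separate device from treatment? Section 3.1 gives statin therapy to both arms, so there is no untreated PET group.

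**How many participants could be affected**

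Inputs: 60 PET participants and a 6-month interval (section 1.3, PET Substudy); accrual of 3 to 4 a month, complete within 50 months (section 3.1).

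Assumptions: PET accrual is even over T months, and there is one switch of system during it. Participants whose baseline falls in the 6 months before the switch have mixed pairs:

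- share f = 6/T
- number = 60 × 6/T

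The first PET scan is at study initiation, so PET participants are new enrolees. If every enrolee joined, the shortest T would be 60/4 = 15 months at 4 a month, or 60/3 = 20 months at 3 a month. The longest is the full 50 months. A switch within 6 months of the start of PET accrual, or within 6 months after its end, would give fewer mixed pairs than 6/T.

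**What a system difference would do**

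If the difference is d, the mean change over all pairs is shifted by f × d. For illustration, let d = b standard deviations of the within-person change, let there be no true change, and apply a two-sided 5% paired z-test to n = 60:

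- SD of observed change = √(1 + f(1 − f)b²)
- δ = f·b·√60 / SD
- rejection rate = 1 − Φ(1.96 − δ) + Φ(−1.96 − δ)

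For T = 15 and b = 0.5: f = 0.40, SD = √(1 + 0.24 × 0.25) = 1.030, δ = 0.20 × 7.746/1.030 = 1.50, rejection rate 0.325.

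| T (months) | f | Mixed pairs of 60 | Bias, b = 0.5 | Rejection, b = 0.5 | Bias, b = 1 | Rejection, b = 1 |
|---|---|---|---|---|---|---|
| 15 | 0.40 | 24 | 0.20 SD | 0.325 | 0.40 SD | 0.795 |
| 20 | 0.30 | 18 | 0.15 SD | 0.205 | 0.30 SD | 0.561 |
| 30 | 0.20 | 12 | 0.10 SD | 0.118 | 0.20 SD | 0.301 |
| 50 | 0.12 | 7.2 | 0.06 SD | 0.074 | 0.12 SD | 0.143 |
| No switch in the PET period | 0 | 0 | 0 | 0.05 | 0 | 0.05 |

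The values of b are assumptions and do not come from the documents.

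**The case against.** The strongest reply is that the number affected may be zero. The unit was only expected during 2011, and PET recruitment dates are not given. That stands: the lower bound is 0, and only a record of the system used for each scan can settle it.

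There are also real mitigations. Dose, uptake time and quantification are standardized, and partial-volume correction is planned. TBR divides by venous blood signal from the same scan, which may cancel a pure scaling difference. It need not cancel differences in resolution or attenuation correction, and SUVmax has no such protection. Comparisons between randomized arms are protected in expectation. A system difference unrelated to LDL or dose would mainly add noise to those correlations. The substudy is a pilot, and FDG uptake is a secondary endpoint.

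A reader might infer more than the text supports:

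- *Calcified FDG-negative plaque becomes ineligible on MR/PET.* The lesion rule does include plaque "and/or with calcification detected by CT and with morphology consistent with that of a plaque", but that is one of several routes. The same section accepts plaque identified on CT or MR, including FDG-negative areas with plaque features on either.
- *The source of the 6-month carotid morphology changes when the new unit arrives.* Appendix B schedules a 6-month carotid MRI for PET participants without any scanner condition, and section 1.3 says the examination uses the standard carotid protocol.
- *Half the participants could be affected by a single switch.* That needs T = 12 months, or 60/12 = 5 a month, above the stated 3 to 4.
- *The switch always runs from PET/CT to MR/PET.* The text sets no changeover date and does not retire PET/CT. If use depended on daily availability, mixed pairs could run either way and 6/T would not describe their share.
- *All the PET aims rest on FDG change.* Aim 5 asks whether FDG activity predicts regression, which baseline FDG can address.

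**Conclusion.** The point holds for analyses of within-person FDG change: the 'between' part of Aim 6, the matching comparisons in section 6.0, and any within-person variability analysis under Aim 7. As written, the plan permits mixed-system pairs and has no means of separating a system difference from the change on therapy within them.

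Under a single switch and even accrual, the share affected is 12% to 40%, or 0 if no switch fell in the PET period. The bias in the overall mean change is that share times a between-system difference that the documents do not give. Same-system pairs, the primary MRI wall-volume endpoint and the expected between-arm difference are not biased. This is an inexpensive improvement to a pilot analysis and does not threaten the trial's main conclusion.

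**What to change.** Section 7.4 says that the study has been in data analysis only since January 2017, so the operative change is to the analysis. Add to the Hypotheses 5, 6 and 7 paragraph of section 6.0:

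1. Record the PET system for every scan and report the number of same-system and mixed pairs.
2. Base the primary analysis of FDG change, and any within-person variability analysis under Aim 7, on same-system pairs only. Report mixed pairs separately.
3. Include system as a covariate in cross-sectional FDG analyses.
4. Measure the regions identified as plaque at baseline again on the 6-month images, so that the same set is compared.

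Had scanning remained, section 1.3 should also have required both scans of a participant on the same system.

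The cost is one variable, one restriction of the analysis set, and some re-reading if the 6-month regions were drawn independently. The downside is the loss of mixed pairs from the change analysis: about 7 of 60 under 50-month accrual, and more if PET accrual was faster. If there are no mixed pairs, one sentence saying so closes the point.

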Coronary arterial imaging will be performed during a 4-5 ml/sec intravenous iodinated contrast (ISOVUE[®]-370) infusion using the following parameters: If heart rate is < 66 bpm prospective ECG gating at 70-80% of one R-R interval, X-ray exposure time ranges from 0.423 - 0.350 sec (depending on heart rate). If heart rate is ≥ 66 bpm prospective ECG gating at 40-80% of two R-R intervals, X-ray exposure time ranges from 1.174 sec - 0.714 sec (depending on heart rate) tube voltage = 120kV, tube current = 300 -580 mA depending on BMI and gender, gantry rotation speed = 0.35 or 0.375 seconds, slice thickness = 0.5 mm, rows = 256-320, range = 128-160 mm. The automated bolus tracking feature will be used to judge contrast bolus arrival and optimize image quality.

The estimated radiation dose for the entire cardiac computed protocol (Calcium scoring (1.5 mSv) + Coronary arterial imaging (3-9 mSv) is 4.5 mSv to 10.5 mSv depending on patient heart rate, BMI, and gender. Betablockers will be used to control the heart rate and thus maintain the radiation dose as low as reasonably achievable. Depending on patient size, a maximum of 2 ml/kg iodinated contrast will be used up to a maximum of 130 ml.

Beta Blockade

In order to optimize image quality by reducing cardiac motion, participants will receive beta blockade on the day of the scan. Participants will have heart rate and blood pressure measured, and will be assessed for contraindications to beta blockade (bradycardia, heart block, active wheezing, history of adverse reaction).

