Informed written consent will be obtained for each participant. Exclusion criteria will include contraindications for CT imaging or contrast administration and arrhythmia.

[figure not shown]
Coronary calcification

Coronary calcification will be measured by the Agatston⁽¹⁰⁾ method, correcting lesion area by the density of calcification in the lesion. A density independent volume score will also be calculated. Total coronary artery calcium scores will be generated by summing the values from the left main, left anterior descending, left circumflex and right coronary arteries. Readers will be blinded to subject identity.

Plaque quantification

Raw data will be reconstructed at 0.5 mm slice-thickness by a multisegment reconstruction algorithm. The baseline axial MDCT images with adequate reconstruction phase will be post processed and analyzed by commercial software (Sure Plaque, Toshiba Medical Systems). Lumen and wall boundaries of target vessels will be semi-automatically detected on cross sectional images. Under the guide of stretched multiplanar reconstructed image (SPR), two experienced readers will review and edit lumen and outer wall contours of coronary segments of the left anterior descending coronary artery (LAD), left circumflex coronary artery (LCX) and right coronary artery (RCA) from ostium to vessel diameter > 2.0mm from cross sectional image by each 1.0 mm in length. Segments with artifact, blur, or stent will be excluded. Volume estimates are obtained by multiplying cross sectional area by slice thickness. Coronary wall volume is computed by subtracting lumen volume from vessel volume.

To quantify coronary lumen volume, vessel wall volume, and total vessel volume by MDCTA we will obtain three indices from MDCTA analysis of the lumen and vessel borders: 1) coronary lumen volume/ vessel volume (LV/VV), 2) coronary wall volume/ vessel volume (WV/VV) and 3) coronary wall volume/ lumen volume (WV/LV) (Fig. 1). The greatest value for all indices obtained for each vessel and patient will be recorded.

T = wall thickness LV= lumen volume VV = vessel volume

Outer contour – volume circumscribed by the outer border of the vessel wall (mm³)

Lumen – volume circumscribed by the inner border of the vessel wall (mm^3)

Wall volume = Outer contour volume – lumen volume (mm³)

PET Substudy

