
Target (plaque) -to-background (blood) ratio (TBR) normalizes vessel wall FDG uptake to the circulating FDG concentration. Once an region of interest (ROI) is defined, either an FDG avid plaque or an FDG negative area with plaque features identified on CT or MR, the TBR is derived from an mean signal within the ROI divided by the mean signal from a large adjacent vein, typically the jugular vein for the carotids and the inferior vena cava for the aorta and iliac vessels.

The target-to-background ratio is calculated:

MDCT Reproducibility Substudy

A subgroup of 60 participants with CT angiography performed in a single R-R interval (scanning heart rate ≤64 bpm) and estimated radiation dosage under 10.5 mSV will return 4 weeks after a protocol scheduled CT for a second reproducibility CT scan. The reproducibility CT angiography will be performed according to the same methods as the baseline imaging (pg 10). Coronary calcium scanning will be omitted to reduce radiation dosage, as the reproducibility of calcium scoring has been well studied. Participants in the reproducibility subset will undergo a total of three CT angiography studies over the 24 month study period. The 10.5 mSv estimated dosage inclusion criterion will ensure that reproducibility patients do not cumulatively receive more than the currently consented radiation dosage limit. In fact, for the reproducibility CT angiogram, scan parameters will be set to limit imaging to a single heartbeat regardless of patient heart rate or arrhythmias. This will ensure that radiation exposure cannot exceed the 21 mSv consented limit for the combination of main protocol and reproducibility substudy angiograms in each study year.

Sixteen to twenty-four patients (total, n=60) will be selected from three groups: (a) patients with a calcium score of 0-99, (b) patients with a calcium score 100-399 and (c) patients with a calcium score of > 400. These 60 scans will be interpreted by two readers, allowing assessment of both intra and interobserver variability as well as repeatability limits.

Inclusion Criteria:

Patients will be selected who had a one RR interval initial CT scan with less than 10.5 mSv estimated radiation dosage.

Exclusion Criteria: Patients who will participate in the PET substudy.

The repeat CT scans will be performed using the same protocol as the initial CT scan. The data obtained from the repeat CT scan will be analyzed in the same manner as that obtained during the initial scan.

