2.0 Eligibility Assessment and Enrollment

2.1 Inclusion Criteria

- A. Men and Women \geq 55 years of age
- B. candidates for lipid lowering therapy under NCEP ATP III guidelines without contraindication to statin therapy
- C. Willing to modify therapy to enroll in the study
- D. Willing to travel to the NIH for follow-up visits.
- E. Able to understand and sign informed consent
- F. Lab Eligibility parameters:
 - eGFR > 45 mL/min/m2
 - For age > 60 test GFR within 1 week prior to contrast; For age <= 60 test within 4 weeks

Inclusion Criteria for the PET Substudy:

Participants who are not participating in the CT Reproducibility study are eligible.

Inclusion Criteria for the Reproducibility Substudy: Patients will be selected who had a one RR interval initial CT scan with less than 10.5 mSv estimated radiation dosage and who will not be participating in the PET Substudy.

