2.3 Screening Evaluation

On- Study Assessments:

Study activities below (see Appendix B for Flow Chart) specify the required study tests and procedures for participants. Baseline visit tests and procedures will be completed 2 weeks before the first dose of study medication, unless otherwise noted. At the baseline visit, the Investigator and/or study staff will:

- A. Review the study procedures and determine that the eligible patient is willing to comply with all protocol requirements;
- B. Review the inclusion and exclusion criteria with the patient and determine if the patient can be a participant in the study;
- C. Record previous and concomitant medications, including vitamin and herbal supplements for the 4 weeks before the first dose of study medication;
- D. Complete patient medical history and physical examination including vital signs, height, and weight;
- E. Collect blood and complete laboratory safety evaluations:
 - Complete blood count (CBC) with platelet and differential,
 - Chemistry Labs: Electrolyte Panel, Creatine, Billirubin (total), Aspartate Amino-Transferase (AST), Alanine Aminotransferase (ALT), Alkaline phosphatase (Alk Phos), Uric acid, Protein (total), Albumin, Calcium, Phosphorous, and Magnesium),
 - 12 hour Fasting Cholesterol (Chol) tests: Chol Total, High density lipoprotein (HDL), Triglycerides, and calculated Low density lipoprotein (LDL)
 - Creatine kinase (CK)
 - High sensitivity C-Reactive Protein (CRP)
 - Urine pregnancy test (for women of childbearing age)
 - Additional 2 tubes of blood will be stored for possible additional testing (not to include genetic or DNA analysis)
- F. Review baseline carotid MRI study regarding feasibility of enrollment;

- G. NIH Pharmacy will randomize patients to protocol.
- H. CT angiography scan will be performed at baseline and at 24 month endpoint. Reproducibility sub-study patients will have an additional CT angiography 4 weeks after either baseline or 24 month scan.
- I. Carotid MRI 0, 12, 24 months both non-contrast and post gadolinium administration. Total scan time will be approximately 1 hour.
- J. Scheduled study visits which are part of the trial expected procedures will be made by one of the Investigators including the Nurse Coordinator. Clinical follow up will be made at the time of one of 7 scheduled clinic visits or in response to notification of any perceived clinical alteration.

Study Calendar – Appendix B

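### The CT reproducibility limits are estimated for one-beat scans only, but section 1.2 would apply them to CT angiography change in general, which includes two-beat scans

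*Combined protocol and SAP*

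**What the plan says.** **Main CT protocol (section 1.3, rest coronary arterial imaging).** Below 66 bpm the scan is gated at 70-80% of one R-R interval. At 66 bpm or more it uses "prospective ECG gating at 40-80% of two R-R intervals". Heart rate is lowered before the scan, with a goal below 60 bpm.

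**Substudy selection (section 1.3, MDCT Reproducibility Substudy).** The group is described as "A subgroup of 60 participants with CT angiography performed in a single R-R interval (scanning heart rate ≤64 bpm"), with an estimated dose under 10.5 mSv. Section 2.1 words the criterion as "Patients will be selected who had a one RR interval initial CT scan", and section 2.2 excludes patients without such a scan.

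**Repeat scan.** Section 1.3 states: "The reproducibility CT angiography will be performed according to the same methods as the baseline imaging". It later says the repeat follows the protocol of the initial scan, and section 7.1 says the same. In between, section 1.3 says that for the repeat "scan parameters will be set to limit imaging to a single heartbeat regardless of patient heart rate or arrhythmias", in order to hold the radiation limit.

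**Timing.** Section 2.3: "Reproducibility sub-study patients will have an additional CT angiography 4 weeks after either baseline or 24 month scan". Section 1.3 refers to any protocol-scheduled CT. Section 7.1 says four weeks after the initial scan.

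**Use and analysis.** Section 1.2 says the data will let investigators determine "whether measured changes in stenoses and plaque morphology exceed that expected from the limits of measurement error in CTA". Section 6.0, Hypothesis 8, plans weighted kappa, ICC and Bland-Altman plots, and does not mention beat mode or heart rate.

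**The concern.** Repeatability limits describe the acquisition conditions under which the pairs were obtained. Here the first scan is selected as one-beat and the repeat is forced to be one-beat. The main protocol allows either mode at baseline and at month 24, so a patient's 24-month change may involve one or two two-beat scans. Nothing in the plan says that the limits do not cover such changes.

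Two further points affect what the 60 pairs represent. A repeat at 66 bpm or more is still taken in one beat, although the main protocol specifies no one-beat window at that rate; pooled with the rest, such pairs blur what the limits measure. And if the initial scan means the baseline scan, a pair that starts at month 24 could join a two-beat scan to a one-beat repeat.

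At stake is the substudy's stated purpose: a measurement-error yardstick that readers can apply to CT angiography change.

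**Working it through.** **1. The plan's own dose figures.** The substudy states no precision or sample-size calculation, so the figures that can be reproduced are the dose and stratum figures.
- Full CT protocol: 1.5 + 3 = 4.5 mSv to 1.5 + 9 = 10.5 mSv, as stated.
- Cumulative limit: 2 × 10.5 = 21 mSv, as stated.
- Calcium-score strata: 3 × 16 = 48 to 3 × 24 = 72, which contains 60.

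**2. Which pairs can arise.**

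| Pair | First scan | Repeat | Mixed beat modes? |
|---|---|---|---|
| Starts at baseline | one-beat by eligibility | one-beat by rule | No |
| Starts at month 24; initial means first scan of the pair | one-beat by eligibility | one-beat by rule | No |
| Starts at month 24; initial means baseline | either mode | one-beat by rule | Yes, if the month-24 scan was at 66 bpm or more |

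The dose limit does not rule out the last row: a month-24 CT at the 10.5 mSv maximum plus a repeat without calcium scan at 9 mSv gives 19.5 mSv, under 21.

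In every row the repeat may be at a faster heart rate than the first scan. At 66 bpm or more, the sentences calling for the same methods or protocol, if read as the full heart-rate rule, lead to two intervals, while the single-heartbeat sentence leads to one.

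**3. Applying one-beat limits to two-beat scans.** Let the one-beat measurement SD be σ and the two-beat SD be kσ. The documents do not give k, so it is an assumption. With normal, independent errors and no bias between modes, the 95% limits for a difference between two one-beat scans are ±1.96·σ·√2.
- Both scans two-beat: the difference has SD kσ√2, so P(outside) = P(|Z| > 1.96/k).
- One scan two-beat: the difference has SD σ√(1 + k²), so P(outside) = P(|Z| > 1.96/√((1 + k²)/2)).

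| k (assumed) | Both two-beat | One two-beat |
|---|---|---|
| 0.8 | 1.4% | 3.0% |
| 1 | 5.0% | 5.0% |
| 1.25 | 11.7% | 8.3% |
| 1.5 | 19.1% | 12.4% |
| 2 | 32.7% | 21.5% |

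Below k = 1 the limits are too wide and real change is missed more often. Above k = 1 they are too narrow.

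**4. If some pairs were mixed.** For a share m of mixed pairs, the pooled limit relative to the pure one-beat limit is √{[2(1 − m) + m(1 + k²)]/2}. With m = 5% to 30% (3 to 18 of 60 pairs) and k = 0.8 to 2, both assumed, this runs from 0.97 to 1.20. For scale, sampling error alone gives a 95% interval of about 0.85 to 1.22 times the estimated within-subject SD from 60 pairs: √(60/χ²) at the 97.5% and 2.5% points of χ² with 60 degrees of freedom.

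**The case against.** The one-beat restriction is deliberate. Section 7.1 gives low radiation as the reason, and the Précis calls the substudy a pilot. This stands as a justification for the design. It does not extend the limits to a mode that was not studied, and no section narrows the conclusion to match.

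The forced single heartbeat protects comparability. With a one-beat first scan, it stops a faster repeat from becoming two-beat. This also stands. A reader might infer that the rule itself creates mixed-mode pairs; for pairs that start at baseline it does the opposite.

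A reader might also infer that month-24 pairs certainly mix modes. The documents do not support that. The opening sentence of the substudy description, and section 7.1, let the initial scan mean the first scan of the pair, and then no pair is mixed. Only the ambiguity is established.

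A reader might see a conflict with the line "Exclusion criteria will include contraindications for CT imaging or contrast administration and arrhythmia". That conflict is weak: an exclusion at entry and a dose cap that holds whatever the rhythm on the scan day can both apply.

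Finally, no planned analysis classifies individual patients as changed. Section 6.0 analyses change with mixed models, and the sentence in section 1.2 is rationale. So the percentages above show how limits used as section 1.2 intends would behave; they are not error rates of a test in this trial. The goal of below 60 bpm may also make two-beat scans uncommon, but no frequency is given.

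**Conclusion.** The concern holds in a limited form. On any reading of the eligibility text, every repeat is one-beat and patients are selected for a one-beat scan, so the limits are not estimated for changes between two-beat scans. They may also include one-beat repeats at rates where the main protocol gives no one-beat window. Section 1.2 would nevertheless use them for CT angiography change in general, and Hypothesis 8 does not separate the pairs.

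The direction of the error is unknown. It would be wrong to conclude that the limits are too narrow, because no section says two-beat scans are noisier. For assumed SD ratios of 1.25 to 2, a stable patient would fall outside the one-beat limits 12% to 33% of the time with both scans two-beat, and 8% to 21.5% with one, against a nominal 5%. At a ratio of 0.8 the figures are 1.4% and 3.0%.

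Mixed-mode pairs are possible on one reading of an undefined word and absent on the other. The differing cut-offs (64 bpm or less in the substudy, below 66 bpm in the main protocol) add a small further ambiguity, for example at 65 bpm.

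**What to change.** 1. Define the eligibility scan as the first scan of the pair, whether baseline or month 24, in sections 1.3, 2.1, 2.2, 2.3 and 7.1. If every first scan meets this, mixed-mode pairs are 0 of 60.
2. In the Hypothesis 8 analysis, use recorded heart rate and beat mode for both scans. Report the repeatability limits for pairs in which both scans were one-beat and below the main-protocol threshold. Show the all-pairs result alongside, and the remaining pairs separately.
3. State in section 1.2 and under Hypothesis 8 that the limits apply only to changes between one-beat scans.
4. Reconcile the same-methods and same-protocol sentences with the single-heartbeat sentence, and the 64 bpm with the 66 bpm cut-off. Which of these governs is for the sponsor to settle.

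Section 7.4 says the study moved to data analysis only in January 2017, so these changes cannot alter how scans were acquired. The index-scan definition then serves to classify pairs already collected, and items 2 and 3 remain fully usable. No scans, radiation or patients are added. The cost is that a few pairs may leave the main estimate, making it somewhat less precise, and that the conclusion is narrower.
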